15.1.4 Documentation and reporting of immediately reportable adverse events

Any SAE that occurs during this trial will be reported (via the "Serious Adverse Event Form") to the Sponsor immediately (i.e., within 24 hours). The information will include at least the following data:

- Name, address, and telephone number of the reporting investigator
- Investigational product(s)
- Trial code
- Patient identification number, sex, and date of birth
- Description of the AE, measures taken and outcome (at the time of reporting)
- Assessment of causality to the IMP by the investigator

Reports will be addressed to:

SCRATCH Pharmacovigilance GmbH & Co. KG
[name]
E-mail: [contact]
[contact]
[contact]

The sponsor ensures to keep detailed records of all AEs which are reported to him by the investigator or investigators. Reporting of SUSARs to the independent ethics committee (IEC) or institutional review board (IRB) and regulatory authorities will follow pertinent national legislation.

The Sponsor will inform as soon as possible and following pertinent national legislation the regulatory authorities and the IECs or IRBs about any event that necessitates reconsideration of the benefit-risk-ratio of the IMP. These events are in particular:

- single cases of expected SARs with an unexpected outcome,
- an increased incidence of expected SARs considered clinically significant,
- SUSARs occurring after a concerned person has completed the trial,

- events related to the conduct of the trial or the development of the tested IMP possibly affecting the safety of the concerned persons.

All additional measures deemed necessary through new findings and taken by the Sponsor or the investigator to protect the safety of the persons concerned and their triggering circumstances will be reported as soon as possible to the concerned regulatory authorities and the IECs or IRBs, if applicable.

Periodic safety reporting to regulatory authorities and the IECs will follow pertinent national legislation.

In the event of a fatality, the "Trial participant's insurer" will be informed by the Sponsor's designee within 24 hours of gaining knowledge of the event. In case of other SAEs, the "Trial participant's insurer" will be informed promptly.

15.1.5 Follow-up of adverse events

All SAEs judged to be related to the IMP must be followed by the investigator until the patient has recovered, recovered with sequelae, died, or until the investigator determines that the patient's condition is stable, whichever occurs first. All other AEs must be followed by the investigator until the conditions mentioned above are met or until the end of the safety follow-up period, whichever comes first, and until all AE-related queries for the patient have been resolved. The investigator will take all appropriate and necessary therapeutic measures required for resolution of the AE, if applicable. All efforts to collect follow-up information must be documented in the source data.

Follow-up information should be supplied on the respective forms of the eCRF.

During and following a patient's participation in this trial, the investigator must ensure that adequate medical care is provided to a patient for any AEs related to the trial, including clinically significant laboratory values.

15.1.6 Handling of anticipated clinical events of COVID-19

Typical COVID-19-related symptoms present at Baseline (examples such as fever, dyspnea, viral pneumonia, or hypoxia) and continuing during the trial without clinically unusual worsening* are considered anticipated clinical events of the underlying condition and will not be collected as AEs. In addition, disease characteristics and severity will be regularly captured within the scope of the clinical status assessment. Death, hospitalization, and use of ventilation, ECMO, or dialysis due to COVID-19 or its complications (which all are recorded as clinical endpoints for this trial) are not considered AEs (see Section 15.1.2) and should not be considered medically significant events by itself for the assessment of SAEs.

Any clinically unusual worsening* of COVID-19-related disease symptoms present at trial inclusion and any clinically relevant changes in clinical laboratory parameters, vital signs or other findings during physical examination which are considered unusual for COVID-19 disease and where a relationship to drug treatment cannot be excluded should be recorded as AEs.

* “Unusual worsening” means that, in terms of type or severity of symptoms, time frame or symptom fluctuations, the course of the disease progression is different from that in most patients with the same general conditions (disease status, age, health status, concurrent diseases).

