- l For assessments, if patients will be discharged from the hospital before Day 14, see *Blinded Treatment period (Day 0 to Day 13) and Day 14 (end-of-treatment)*. For centers in Bulgaria only: Patients must be hospitalized during the entire treatment period.
- m Within 4 days of randomization.
- n If no EoS visit was performed, information about patient status should be reported on the EoS page in the case report form. If the patient is lost to follow-up, the investigator must contact the patient, the patient's family or the referring physician by phone or email to obtain survival status, or it must be possible to search in registers or publicly available information for these survival data.
- o Blood sampling must be performed in the morning around the time the morning dose was usually taken by the respective patient.
- p Safety follow up assessments must be performed regularly (at least once) by phone or email between Day 28/EoS and Day 60 and documented as an unscheduled visit in the eCRF. The patients should be asked to return for an on-site visit if the investigator deems this necessary for follow-up. The assessments not to be done if the visit is performed as a telephone or email contact in the scope of the safety follow up are marked as •^p
- q *Optional for centers in the USA only: 2 blood samples will be collected to evaluate immune cell subtypes and immune reactions for future research studies. This will be shipped directly to a US research site and not to the central laboratory. Shipment needs to be done at ambient temperature and immediately the same day after sampling.*
- r Height and weight only to be measured at D0, pre-dose.

AE = adverse event, CT = computed tomography, cont. = continued, D = day, ECG = electrocardiogram, ECMO = extracorporeal membrane oxygenation, EoS = end-of-study, EoT = end-of-treatment, ICU = intensive care unit, Ig = immunoglobulin, IMP = investigational medicinal product, incl. = including, interst. = interstitial, pre(post) = pre(post) IMP, RRT = renal-replacement therapy, Radiol. = radiological, SARS-CoV-2 = severe acute respiratory syndrome coronavirus 2, SFU = safety follow up, SoC = standard of care, SpO₂ = peripheral capillary oxyhemoglobin saturation, ventil. = ventilation, USV = unscheduled visit, WHO = World Health Organization.

12.2 Screening (Day -2 to Day 0) and Day 0

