12.6 Safety follow-up

Following the D28/EoS examination, the investigator will contact the patient regularly (at least once) by phone or email to obtain health data until Day 60. This should be documented as an unscheduled visit in the eCRF. The patients should be asked to return for an on-site visit if the investigator deems this necessary for follow-up.

13 Efficacy and baseline assessments and procedures

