15.1.1.3 Serious adverse events

An SAE is any untoward medical occurrence that, at any dose:

- results in death
- is life-threatening
- requires inpatient hospitalization or prolongation of existing hospitalization
- results in persistent or significant disability or incapacity
- results in a congenital abnormality or birth defect

NOTE: The term "life-threatening" in the definition of "serious" refers to an event in which the patient was at risk of death at the time of the event; it does not refer to an event, which hypothetically might have caused death, if it were more severe.

Medical and scientific judgment will be exercised in deciding whether expedited reporting is appropriate in other situations, such as important medical events that may not be immediately life-threatening or result in death or hospitalization, but may jeopardize the patient or may require intervention to prevent one of the other outcomes listed in the definition above. These will usually also be considered serious.

Examples of such events are intensive treatment in an emergency room or at home for allergic bronchospasm; blood dyscrasias or convulsions that do not result in hospitalization; or development of drug dependency or drug abuse. In addition, new malignancies that occur during the participation in the trial are defined as important medical events and must be reported as SAEs.

An SAE requires that the underlying event is considered an AE as defined in Section [15.1.1.1](#).

Hospitalizations due to a surgery or procedure during the trial will not be considered an SAE if the surgery or procedure will be performed for a pre-existing condition and the surgery or procedure was planned prior to trial entry. However, if the pre-existing condition deteriorates unexpectedly during the trial (e.g., surgery performed earlier than planned), then the deterioration of the condition leading to hospitalization will be considered an SAE. Hospital admission for social, quarantine, or convenience reasons will not be recorded as SAE. Hospitalization and death due to COVID-19 are anticipated clinical events of the underlying disease and cannot be used as reason for SAE classification without an underlying AE leading to hospitalization or death (see also Section 15.1.6).

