15.1.3 Documentation of adverse events

All AEs occurring between the time written informed consent was obtained and until the end of the safety follow-up period (safety observation period) must be recorded. Information on AEs will be derived by non-directive questioning of the patients in general terms at each visit if possible (e.g., "How do you feel?" or "How have you been since the last questioning?"), by patients' spontaneous reports, or by observation. Adverse events also may be detected when they are volunteered by the patient during or between assessments and/or visits or through physical examination, laboratory test, or other assessments.

* Instrumental ADL refer to preparing meals, shopping for groceries or clothes, using the telephone, managing money, etc.

** Self care ADL refer to bathing, dressing and undressing, feeding self, using the toilet, taking medications, and not bedridden.

All AEs that occur during the safety observation period of the trial as described above will be recorded in the patient's AE section of the eCRF and will include the following information: a description of the AE, date of onset and resolution, severity, relationship to the IMP, relationship to trial procedure, action taken, and outcome. For SAEs, the SAE form must be completed (see Section 15.1.4).

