The following imputation of concurrent events in the preferred analysis of ICU duration, creating the most conservative assessment approach will be performed: a) for all death cases that have no recorded or known ICU hospitalization in this trial, start date will be imputed as date/time of death, end date will be imputed as Day 28 b) if ICU treatment is known and started before the date of death, start date will be the actual ICU submission, end date will be imputed as Day 28.

For patients who are lost to follow-up or discontinue the trial on or before Day 13 (last treatment day) due to any reason other than death and patients who discontinue with a last observed WHO clinical status no lower than that at Screening, the following approach will be performed: a) for cases that have no recorded or known ICU hospitalization in this trial, start date will be imputed as date/time of discontinuation, end date will be imputed as Day 28 b) if ICU treatment is known and started before the date of study discontinuation, start date will be imputed as actual ICU submission, end date will be imputed as Day 28.

As sensitivity analyses, ICU duration imputation on available data will be done as follows:

- for patients who died, the study period of 28 days will be recorded as ICU treatment duration,
- for patients who discontinued the study prematurely or for patients who died before EoS, the available information on ICU treatment duration until day of discontinuation will be used.

In Part 1, the ICU duration will be displayed with basic statistics per stratification factor age (< or \geq 65 years) and antiviral therapy (no antivirals, Hydroxychloroquine and Chloroquine, all other antivirals) and overall. In addition, an exact 2-sided 90% confidence interval for the median of differences between treatment groups (location shift) will be conducted adjusted for the stratification factors age and antiviral therapy.

28-day all-cause mortality

28-day all-cause mortality will be derived as percentage of patients who died due to any cause from time of 1st IMP administration until EoS. In Part 1, 28-day all-cause mortality will be displayed with frequency tables per stratification factor age (< or \geq 65 years) and antiviral therapy (no antivirals, Hydroxychloroquine and Chloroquine, all other antivirals) and overall. In addition, an OR with exact 2-sided 90% confidence interval will be conducted. The OR will be calculated adjusted for the stratification factors.

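### The AE exemption for COVID-19 death, ventilation, ECMO and dialysis has no end day, but the main endpoints it leans on stop at Day 28, so capture to Day 60 is only partial and indirect

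*Combined protocol and SAP*

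**What the plan says.** Section 15.1.6 lists the events "Death, hospitalization, and use of ventilation, ECMO, or dialysis due to COVID-19 or its complications (which all are recorded as clinical endpoints" and says that they "are not considered AEs (see Section 15.1.2) and should not be considered medically significant events by itself for the assessment of SAEs". Section 15.1.1.3 adds that hospitalization and death due to COVID-19 "cannot be used as reason for SAE classification without an underlying AE leading to hospitalization or death". One exception is kept: "Any clinically unusual worsening* of COVID-19-related disease symptoms present at trial inclusion" is still to be recorded as an AE.

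Section 16.3.2 defines 28-day mortality as the "percentage of patients who died due to any cause from time of 1st IMP administration until EoS". In Section 7 the primary endpoint, the other key secondary endpoints and the RRT-free and ECMO-free proportions also run to EoS or earlier.

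Safety observation runs longer. Under Section 15.1.3, AEs from consent "until the end of the safety follow-up period (safety observation period) must be recorded". Under Section 12.6, "the investigator will contact the patient regularly (at least once) by phone or email to obtain health data until Day 60", with an on-site visit only if the investigator thinks it necessary. Footnote p to Tables 1 and 3 flags "The assessments not to be done if the visit is performed as a telephone or email contact".

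**The concern.** The exemption is reasonable while the events are being counted elsewhere. After Day 28 the main endpoints no longer count them, yet the exemption continues. If the follow-up schedule does not pick them up, a COVID-19 death or a start of organ support between Day 29 and Day 60 may leave no structured entry. The safety follow-up was added to extend observation, and all-cause mortality by arm is the simplest safety summary it could give. An excess of deaths that each look typical for COVID-19 is also what case-by-case AE judgement is least likely to show; a plain count by arm would show it.

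**Working it through.** **Length of the window.** The synopsis gives 14 days of treatment, 14 days of follow-up and 32 days of safety follow-up: 14 + 14 + 32 = 60, which matches Day 60 in Section 12.6. The part after EoS is 60 − 28 = 32 days, or 32/60 = 53% of the time after Day 0. This measures time, not events lost.

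**What is recorded after Day 28.** The AE rules (15.1.1.3, 15.1.6), the endpoint windows (7, 16.3.2) and the unscheduled-visit/SFU column of Tables 1 and 3 compare as follows.

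| Event due to COVID-19 | Endpoint window | AE/SAE in its own right? | Due at phone/email contact? | Due at on-site SFU visit? |
|---|---|---|---|---|
| Death | 28-day mortality: to EoS | No | No survival mark | No survival mark; WHO score only |
| Ventilation | Need for INV: to EoS | No | No (p flag) | Yes |
| RRT/dialysis | RRT-free: to EoS | No | No (p flag) | Yes |
| ECMO | ECMO-free: to EoS | No | No (p flag) | Yes |
| Hospitalization/ICU | ICU duration: to EoS | Hospitalization: no | Yes | Yes |

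Concomitant medications/procedures and AE assessment are also marked in the SFU column without the p flag, so they are due at every contact. Time to death and the durations of INV, RRT and ECMO have no end day in Section 7, but no scheduled survival field would supply deaths after Day 28.

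The tables were extracted from PDF, so column positions are inferred from the row patterns. The revision chronology agrees with this reading: it names hospitalization/ICU status among the SFU additions, does not name survival, and says RRT and ECMO are not noted at a telephone visit.

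**Survival tracing.** Section 12.5 and footnote n provide for contacting family or physicians, or searching registers, when the EoS visit is missed. Section 12.6 has no counterpart.

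**Illustration.** A patient ventilated at Day 28 dies of a typical COVID-19 course on Day 38. The patient counts as alive for 28-day mortality. The death is not an AE or SAE by itself, and no survival field is scheduled. Hospital or ICU status, concomitant procedures and perhaps the discontinuation page may still reveal it.

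**Timing of contact.** The minimum is one contact. On Day 29 it covers 29 − 28 = 1 day after EoS; on Day 60 it covers 60 − 28 = 32 days. Either meets the minimum count.

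**Related mismatches.** Section 15.1.1.1 ends the safety monitoring period at the EoS visit, while Section 15.1.3 ends safety observation with the SFU. Section 11.2 documents medications only to EoS, while Tables 1 and 3 mark them at the SFU.

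**The case against.** A reader might infer that these events enter no record at all after Day 28. The documents do not support that. Intubation and dialysis are procedures, and procedures, hospital/ICU status and AEs are due even by phone. On-site visits schedule ventilation type, RRT, ECMO and WHO score. Section 22.1 requires all data generated after consent to be in the eCRF. Section 17.2 lists COVID-19 death as a discontinuation reason to be recorded; whether that page applies once EoS is complete is not stated. The unscheduled-visit eCRF page is not shown and might hold a death field. The illustrated patient may also still be in the trial hospital, where the phone exemption need not apply.

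A reader might also infer that late renal failure would be invisible. It would not necessarily be. Section 15.1.6 exempts dialysis due to COVID-19, not renal failure itself. Exclusion criterion 17 removes known acute or clinically relevant chronic renal failure at entry, so new renal failure is not a continuing baseline symptom and can be an AE. Unusual worsening also includes an unusual time frame.

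On timing, the text says regular contact, Section 15.1.3 also accepts spontaneous reports, and the AE duty does not end with the first call. One day of coverage is thus the literal minimum for contacts, not the limit of AE reporting.

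Finally, dosing ends on the evening of Day 13. By Day 28 about 15 × 24 = 360 hours have passed, or 360/40 = 9 to 360/30 = 12 half-lives at the 30 to 40 hours given in Section 5.2.2. Late drug-related events become less likely, though not excluded.

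These points narrow the concern. They do not supply a survival field, an organ-support question at the default contact, or an end day for the exemption. On-site visits are discretionary, a patient who has died cannot attend one, and unusual worsening by definition leaves out a typical fatal course.

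**Conclusion.** The point holds in limited form. From Day 29 to Day 60, COVID-19 death, ventilation, ECMO and dialysis remain outside AE/SAE reporting in their own right and outside the Day 28 endpoints. Survival has no scheduled field, and organ support is scheduled only on site. What remains is partial and indirect, so Day 60 all-cause mortality and late organ support by arm cannot be relied on.

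The window is 32 days. It would be wrong to read 53% as the share of events lost: the documents give no event rate after Day 28. Section 8.2 puts recovery or death at an average of 22 days without a distribution, which makes some courses beyond Day 28 plausible but does not count them.

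The conclusion assumes that the table columns are read correctly and that the eCRF page follows the tables. The primary and 28-day analyses are unaffected. The change is worth making because the period exists for safety and the gap is cheap to close.

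**What to change.** 1. Tables 1 and 3: add survival status (date and cause of death) to the SFU column, and add a yes/no question on INV, RRT or ECMO since the last contact, with dates, to be asked by phone or email.
2. Section 12.6 and footnote p: place the last required contact at or near Day 60; earlier contacts can stay optional.
3. Section 15.1.6: either limit the exemption to events up to Day 28/EoS, or state that later events are recorded on the SFU page.
4. Reconcile Section 15.1.1.1 with 15.1.3 on the end of safety observation, and Section 11.2 with the tables on medications.

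A descriptive table of Day 60 all-cause mortality by arm would then follow from the data. It is optional, since 28-day mortality is the chosen endpoint.

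The cost is a few entries on an eCRF page that already exists and a target date for a contact already required. If later events are reported as SAEs rather than on the SFU page, there would be a few more reports.

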15.1.7 Further safety precautions

Patients known or suspected to have Gilbert syndrome should be carefully monitored, and any clinically relevant increase in bilirubin, in particular indirect bilirubin, in these patients should be carefully considered in terms of benefit-risk assessment.

A daily supplementation of either 2 x 750 mg oral bicarbonate or 2 tablets of Neoralit SR three times daily during meals or half an hour after meals is recommended for patients with

- Known history of nephrolithiasis
- Underlying condition with a strong association of nephrolithiasis, including hereditary hyperoxaluria or hereditary hyperuricemia
- History or clinical diagnosis of gout

15.1.8 Pregnancies

Should a pregnancy occur in a female patient, or in a female partner of a male patient, it must be reported to the Sponsor within 24 hours of the first awareness of the event and be recorded on the appropriate pregnancy form. The trial participation of patients who become pregnant during the trial after signing the informed consent will be discontinued immediately.

A pregnancy is not regarded an AE unless there is a suspicion that the IMP may have interfered with the effectiveness of a contraceptive method. Whenever possible, the outcome of all pregnancies (spontaneous miscarriage, elective termination, normal birth or congenital abnormality, maternal and/or new-born complications) must be followed up and documented even if the patient was discontinued from the trial. All reports of congenital abnormalities or birth defects are SAEs. Spontaneous miscarriages will also be reported and handled as SAEs. Elective abortions without complications will not be handled as AEs.

Pregnancy follow-up will be recorded on the pregnancy form and will include an assessment of the possible relationship of the IMP to any pregnancy outcome.

